2.2.2 Summary of Potential Risks and Benefits

For prolonging disease-free survival, potential benefits of an early treatment strategy of initiating ART at a CD4+ cell count > 500 cells/mm³ are:

- Maintenance of a higher CD4+ cell count
- Lower risk of AIDS and non-AIDS conditions

Potential risks of the early ART strategy are:

- More side effects
- Increased risk of exhausting drug options (e.g., due to resistance)
- Increased risk of some non-AIDS events.

For prolonging disease-free survival, potential benefits of a deferred ART strategy that stipulate that ART be initiated when the CD4+ cell count declines to < 350 cells/mm³ are:

- Drugs that are safer, easier to take, and more potent and/or less susceptible to resistance development could be available when ART is eventually initiated
- Delay in any risk of adverse events of ART

Potential risks of this strategy include:

- Longer period of time at lower CD4+ cell counts and higher HIV RNA levels
- Higher risk of AIDS and serious non-AIDS conditions while ART is deferred

In addition to these potential benefits and risks of early ART for patients with a CD4+ cell count > 500 cells/mm³, there is a potential broader public health benefit of early ART. As noted in [Appendix B](#), even if transmission risk behaviors do not decrease among patients taking early ART, reduced HIV transmission would be predicted based on HIV RNA decline with ART.

2.3 Rationale for Selected Study Design

2.3.1 CD4+ Cell Count Entry Criteria and CD4+ Count Deferral Criteria for Control Group

The immediate and deferred ART strategies need to be sufficiently different in their definition so that a difference in clinical outcomes between them is plausible. Thus, the CD4+ cell count entry and deferral criteria were selected to result in groups with substantially different exposure to ART over the planned follow-up period.

At entry, participants will have a CD4+ count > 500 cells/mm³. ART will be initiated in the deferred ART group when the CD4+ declines to < 350 cells/mm³. The deferral strategy was chosen with consideration of current practice and recent data from SMART^{11,14} that indicate that initiation of ART should take place closer to 350 than 200 cells/mm³. If the majority of participants enrolled have a CD4+ cell count between 500 and 650 cells and CD4+ declines on average 50-60 cells/mm³ per year in the absence of ART, the majority of participants in the deferred ART group are likely to remain off ART for at least 2-3 years of follow-up.²⁵

As a consequence of the CD4+ entry and ART deferral criteria, and considering the rate of CD4+ increase following initiation of ART and the magnitude of the increase starting at lower versus higher CD4+ levels, these two strategies for initiating ART will result in treatment groups with substantially different CD4+ cell counts and HIV RNA levels over a 5-year follow-up period.

2.3.2 Broad Entry Criteria

With few exceptions, any healthy HIV-infected adult with a CD4+ cell count > 500 cells/mm³ at two visits within 60 days before randomization who has not taken ART or interleukin-2 (IL-2) is eligible to enroll. Participants may have had a prior CD4+ count ≤ 500 cells/mm³, and this will be recorded. The participant may have any HIV RNA level. HIV RNA level predicts the rate of CD4+ decline.^{26,27} Thus, on average, participants with higher HIV RNA levels in the deferred ART group are likely to meet the CD4+ threshold for ART (350 cells/mm³) more rapidly than those participants with lower HIV RNA levels. Restricting enrollment to participants with high HIV RNA could result in less distinguishable treatment groups in terms of ART use and miss an opportunity to assess whether risk of serious non-AIDS diseases associated with HIV RNA, even at low levels, can be reduced with ART. While excluding participants with high HIV RNA levels would, on average, increase the difference in ART exposure between groups, HIV RNA does not explain a large fraction of the variability in the CD4+ decline.²⁷ Thus, rapid decline in CD4+ is still likely for some participants. The exclusion of participants with high HIV RNA would eliminate a large subgroup of participants for which there is uncertainty about when to start ART and limit ability for risk stratification. These broad entry criteria are likely to result in the inclusion of a group of participants at variable risk for the composite endpoint. This will permit risk stratification to be carried out at the completion of the study to determine how ART should most effectively be used in subgroups considering absolute risk reductions and cost effectiveness.

2.3.3 Composite Endpoint of AIDS* and Non-AIDS

The ultimate goal of the treatment of HIV disease is to prevent morbidity and mortality. Thus, the primary and secondary endpoints of this study are clinical outcomes rather than surrogate markers.

The primary endpoint of the START study is a composite outcome of AIDS*, non-AIDS, and death from any cause (see [Appendix E](#)). This composite outcome includes major morbid events that are life threatening and impact quality of life.

It is hypothesized that ART will positively influence both AIDS* and non-AIDS risk in the CD4+ range to be studied. Based on epidemiological studies, ART is expected to reduce the risk of AIDS* more than the risk of non-AIDS. However, the incidence of non-AIDS is expected to be greater than the incidence of AIDS*. Thus, the absolute risk reduction is expected to be similar for AIDS* and non-AIDS events.

2.3.4 Major Secondary Outcomes

2.3.4.1 Secondary Clinical Outcomes

A number of secondary outcomes will be assessed at interim and final analyses to allow for the careful weighing of the benefits and risks of early ART. These clinical outcomes include the separate components of the composite outcome; all-cause mortality; all AIDS events (including esophageal candidiasis and chronic *Herpes simplex*); all non-AIDS-defining cancers (including basal and squamous cell skin cancers); bacterial pneumonia; pulmonary embolism; deep vein thrombosis; new-onset diabetes mellitus; coronary artery disease requiring drug treatment; congestive heart failure; peripheral vascular disease; fractures; and adverse events.

2.3.4.2 Quality of Life, Health-Care Utilization and Cost of Care

Quality of life will be assessed using the self-administered Medical Outcomes Study Short-Form 12 Item Survey (SF-12, version 2) and a visual analog scale for current health (zero to 100, with zero being worst possible health).^{28,29,30} A comparison of the costs and cost effectiveness of early versus deferred ART will be a critical component of the START study. The eventual implications of START for HIV care may rest on cost-effectiveness analysis. The majority of the costs of medical care among study participants will probably be those of ART, because hospitalizations and other expensive clinical interventions (e.g., nursing home care) are predicted to be quite uncommon in the study population. ART costs will be assessed from detailed information on usage in the two study arms and can be compared in a number of sensitivity analyses using different drug pricing systems (e.g., Average Wholesale Price [AWP], Public Health Service [PHS] price, and generic price). Geographic differences will be considered. Non-ART drugs will likely be only 5% of ART costs, and therefore, will not be collected in detail. Health-care utilization (hospitalization, clinic visits, nursing home care, and home care) will be reported and then used to estimate costs. Indirect costs of medical illness will also be estimated.

2.3.4.3 Transmission Risk Behavior

Information will also be collected on high-risk behaviors for transmitting HIV. Epidemiological data indicate that risk of sexual transmission of HIV is closely related to plasma viral load.^{31,32} Thus, early ART may effectively lower risk of transmission if risk behaviors are similar in the two treatment groups.

2.3.4.4 HIV Drug Resistance

The development of resistance to ART and possible subsequent loss of drug options will be assessed as an important secondary outcome in the study. This outcome will be

evaluated by collecting samples of blood prior to changes in ART due to elevated HIV RNA level and by collecting results from locally performed resistance tests. The former will be used to carry out batch resistance testing at a central laboratory during the trial. These tests will not be done in real time, and results will not be given to the investigator or participant. Key mutations that are associated with viral resistance will be determined using information periodically updated by the International AIDS Society.³³ The early and deferred ART groups will be compared for the accumulation of major mutations to each class of ART.

2.3.4.5 Markers of CVD risk

Assessments will be made of blood lipids, smoking, blood pressure, resting electrocardiographic (ECG) abnormalities, incidence of diabetes mellitus, use of medication to lower blood pressure and lipids, and the use of aspirin, to assist in the evaluation of cardiovascular risks and benefits of early treatment. For all consenting participants, plasma will be stored for central measurement of inflammatory and coagulation markers.

2.4 Summary

For HIV-infected individuals with a CD4+ cell count > 500 cells/mm³ who are not taking ART, there is genuine uncertainty whether the risk of morbidity and mortality from non-AIDS conditions that may result from ongoing viral replication and consequent general immune activation or immunodeficiency at higher CD4+ levels can be modified with ART. The findings from SMART suggest that risks of AIDS* and non-AIDS events could be reduced by initiating ART among patients at CD4+ cell counts > 350 cells/mm³. However, it is unclear whether the findings from SMART can be generalized to ART-naïve patients or to patients with counts > 500 cells/mm³. Epidemiological studies also suggest that reduced risks of AIDS and of some non-AIDS conditions would result from early ART. However, as in other illnesses, it is hazardous to assume that people's risk of disease can be modified with ART as predicted by the epidemiological data.

The risk of non-AIDS events is higher than the risk of AIDS* events in these patients. START will, therefore, assess these risks and determine the effectiveness of early ART in reducing the rate of a composite outcome that includes both AIDS* and non-AIDS. START will expand our understanding of how immunodeficiency and immune activation influence the risk of development of both AIDS* events and, more importantly, non-AIDS events at high CD4+ levels.

If START establishes that ART is beneficial among individuals with a CD4+ cell count > 500 cells/mm³ for a broad range of health outcomes, the earlier use of ART in many parts of the world would be based on cost-effectiveness analyses, based both on the effectiveness of ART in the patients being treated and any effects in reducing the rate of ongoing transmission.

The potential for large reductions in morbidity and mortality with early ART is great; there is substantial uncertainty as to whether the risk reduction suggested by the epidemiological data and SMART results will be realized; and there is a high probability

of being able to enroll and follow patients and carry out the planned early intervention. Therefore, the timing for a randomized trial is ideal.

3 Methodology

3.1 Study Design

This is a multicenter, international, randomized trial for HIV-infected adults comparing initiation of ART at a CD4+ cell count > 500 cells/mm³ (early ART) versus initiation of ART at a CD4+ cell count of < 350 cells/mm³ (deferred ART) for a composite outcome of AIDS*, non-AIDS, and death from any cause (see [Appendix E](#)).

In addition to the composite outcome, two important secondary outcomes will be evaluated: (1) AIDS* or death from AIDS; and (2) non-AIDS or death not attributable to AIDS, including death of unknown cause. Other secondary outcomes include components of the major endpoints, HIV drug resistance, quality of life, cost effectiveness, and HIV transmission risk behaviors.

With few exceptions, consenting, asymptomatic, ART-naïve participants 18 years of age or older with a CD4+ cell count > 500 cells/mm³ are eligible for randomization to the trial.

Participants in the early ART arm will commence ART immediately following randomization and continue taking it for the duration of the trial. Participants in the deferred ART group, the control arm, should commence treatment when the CD4+ declines to < 350 cells/mm³ or if an AIDS-defining diagnosis occurs. In addition, when certain other conditions or symptoms occur as specified by local guidelines, ART may be initiated. In this study, when the CD4+ declines to < 350 cells/mm³ for a participant in the deferred arm, the CD4+ count will be immediately confirmed (within 4 weeks), and if the second CD4+ count is also < 350 cells/mm³, ART will be initiated.

For participants in both treatment groups, the initial regimen used must be chosen from those listed on the INSIGHT website table “Antiretroviral Components Required for the Initial Regimen in START.” This table is based on current DHHS guidelines and will be updated as guidelines change (see [Appendix H](#)).

3.2 Study Objectives

3.2.1 Primary Objective

To determine whether early ART is superior to deferred ART in delaying the occurrence of a composite outcome consisting of AIDS*, non-AIDS, or death from any cause.

3.2.2 Secondary Objectives

- a. To compare early ART to deferred ART for each component of the primary composite endpoint:
 - AIDS* or death from AIDS
 - Non-AIDS or death not attributable to AIDS

- b. To compare early ART to deferred ART for the following secondary outcomes:
- All-cause mortality
 - Non-AIDS
 - CVD (myocardial infarction, stroke, coronary revascularization)
 - ESRD (initiation of dialysis, renal transplantation)
 - Decompensated liver disease
 - Non-AIDS malignancy, excluding basal and squamous cell skin cancers
 - Non-AIDS malignancy, including basal and squamous cell skin cancers
 - AIDS
 - Bacterial pneumonia
 - Adverse events
 - Hospitalization
 - Quality of life
 - Health-care utilization and cost of care
 - HIV transmission risk behavior
 - HIV drug resistance
 - Pulmonary embolism or deep vein thrombosis
 - New-onset diabetes mellitus
 - Coronary artery disease requiring drug treatment
 - Congestive heart failure
 - Peripheral arterial disease
 - Change in estimated GFR and development of proteinuria
 - Blood pressure and blood lipids
 - ECG abnormalities
 - Use of blood pressure- or lipid-lowering treatment or aspirin
 - Fractures
- c. To compare early ART with deferred ART for the primary composite outcome and other major clinical outcomes in subgroups defined by the following characteristics measured at baseline:
- Age
 - Gender
 - Race/ethnicity
 - Presence and levels of risk factors for serious non-AIDS conditions (e.g., smoking, estimated GFR (eGFR), hepatitis co-infection, diabetes mellitus, estimated CVD risk, lipids, blood pressure, presence of resting ECG abnormalities, age, and gender)
 - Baseline CD4+ cell count
 - Baseline HIV RNA level
 - Geographic region
 - Calendar date of enrollment
 - ART regimen specified prior to randomization

3.2.3 Other Objectives

For a robust comparison of the early and deferred ART groups, the groups must differ by a substantial amount in exposure to ART during follow-up. The first three objectives listed below are aimed at understanding whether protocol assumptions are valid and at evaluating adherence to the protocol.

- a. To compare the early and deferred ART groups for:
 - ART use over follow-up
 - HIV RNA levels over follow-up
 - CD4+ cell counts over follow-up
- b. To describe the early and deferred groups with respect to:
 - Initial ART regimen used
 - HIV RNA and CD4+ cell count response to the initial ART regimen
 - Number of changes in ART regimen over all follow-up and during the first year of treatment
 - Non-adherence to treatment strategy (e.g., discontinuation of ART in early ART group or initiation of ART too early in the deferred group)
- c. Among participants in the deferred group, to estimate the rate of decline of CD4+ cell counts until the CD4+ declines to < 350 cells/mm³, to estimate the fraction of participants who develop a primary event prior to starting ART, to estimate time to first ART initiation, and to estimate the fraction of participants who initiate ART before the CD4+ declines to < 350 cells/mm³
- d. Among participants in both treatment groups, to study predictors of AIDS* and non-AIDS
- e. To estimate the prevalence and levels of non-AIDS risk factors at baseline (e.g., smoking, eGFR, hepatitis co-infection, diabetes mellitus, estimated CVD risk, lipids, blood pressure, presence of resting ECG abnormalities, age, and gender)
- f. To evaluate the informed consent process by comparing comprehension of study requirements for those consented with a concise versus standard consent (in a subset of sites)

3.3 Primary Study Endpoint

The primary composite endpoint is defined in [Appendix E](#) and includes the following three major components:

- AIDS* or death from AIDS
Opportunistic events consistent with the 1993 CDC expanded surveillance definition plus additional events associated with immunosuppression in the patient population targeted for enrollment. Esophageal candidiasis and chronic *Herpes simplex* infection will be counted as primary endpoints only if they result in death.

- Non-AIDS
 - CVD: myocardial infarction, stroke, coronary revascularization
 - ESRD: initiation of dialysis, renal transplantation
 - Decompensated liver disease
 - Non-AIDS-defining cancers, excluding basal and squamous cell skin cancers. Basal and squamous cell skin cancer will be counted as a primary endpoint only if they result in death.
- Death not attributable to AIDS, including death of unknown cause

The primary outcome of START and each of the major components of the primary outcome will be evaluated as the time to the first occurrence of an event above. Other major endpoints are referred to in the Study Objectives (section 3.2).

3.4 Randomization

Eligible participants will be randomized in a 1:1 ratio to either the early ART group or the deferred ART group. Randomization will be stratified by clinical site.

3.5 Sample Size and Statistical Considerations

It is estimated that 4,000 participants will be required to reliably address the primary study question. This is based on estimates of the expected event rates in the early and deferred ART groups using data from the CASCADE Collaboration and UK CHIC³⁴ with computer simulations that account for the distribution of CD4+ cell counts projected for START. These estimates and other assumptions used in calculating sample size are described in detail in [Appendix G](#) and summarized below:

- a. The primary analysis will be intention to treat using a Cox model with a single indicator for treatment group and with strata corresponding to geographic regions (North America, South America, Europe, Australasia, and Africa).
- b. Type I error is 0.05 (2-sided) and power = 0.90. Power was set at 90% for the primary endpoint, in part, to ensure that there would be adequate power to address the components of the composite endpoint, non-AIDS and fatal AIDS or non-fatal AIDS*.
- c. Participants will be enrolled over a 3-year period (2 additional years after the one year pilot phase) and followed for a minimum of 3 years resulting in an average follow-up of 4.5 years and a total study duration of 6 years.
- d. The CD4+ cell count at entry will be between 501 and 600 cells/mm³ for 70% of participants, between 601 and 700 cells/mm³ for 20%, and > 700 cells/mm³ for 10%.
- e. In the deferred ART group, the rate of the primary endpoint is 2.8 per 100 person years over the follow-up period. Non-AIDS events will be four times more common than non-AIDS deaths, and approximately 35% of reported AIDS events and 10% of

reported non-AIDS events will not meet probable or confirmed criteria (i.e., the criteria that have to be achieved to count the reported event as an endpoint). In SMART, the rates of confirmed or probable fatal AIDS or non-fatal AIDS* and of serious non-AIDS, as defined in START, were 0.4 and 2.0 per 100 person-years, respectively, in the VS group.³⁵

- f. Based on the computer simulations described in [Appendix G](#), early ART is predicted to reduce the primary endpoint rate by 28.8% compared to deferred ART. This reduction in the hazard assumes: (1) AIDS* events represent 23% of the events in the deferred arm, and early ART will reduce this hazard by 43%; and (2) non-AIDS events and deaths not attributable to AIDS will represent 77% of events in the deferred ART group, and early ART will reduce this hazard by 24%. The smaller percentage risk reduction anticipated for non-AIDS events and deaths not attributable to AIDS takes into account that some of the deaths will be due to causes that are unrelated to HIV and ART. For example, 18% of deaths in SMART were due to substance abuse, accidents or violence.¹¹
- g. The estimated treatment differences take into account likely levels of adherence to the early ART strategy (e.g., participants followed in CASCADE who started ART were considered “on ART” irrespective of adherence or future discontinuation of their ART).
- h. Adherence to the deferred strategy was also considered. It was assumed that 70% of participants would adhere to the deferral CD4+ threshold of 350 cells/mm³ and 30% would initiate ART earlier – 10% before the CD4+ declined to 400 cells/mm³ and 20% while the CD4+ was between 350 and 400 cells/mm³.
- i. A loss to follow-up rate of 2.7 per 100 person-years (equivalent to a 15% cumulative lost to follow-up after 6 years) is assumed.
- j. Based on these assumptions, 3,822 participants (1,911 participants in each treatment group) are required. The number of primary events required is 369.
- k. While many of the underlying assumptions are conservative, for some assumptions there is much uncertainty because of the absence of data (e.g., inadequate or no data on rates of non-AIDS morbidity). Considering this, a sample size of 4,000 participants (2,000 in each treatment group) and a target of 370 primary events has been established as the initial goal. This may be modified following sample size re-estimation.

Power was also estimated for the components of the primary endpoint. With the above assumptions, and with 4,000 participants and 370 primary events, power is 0.74 to detect a 43% reduction in the hazard of AIDS*, and power is 0.73 to detect a 24% reduction in the hazard of non-AIDS and deaths not attributable to AIDS.

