The early and deferred ART groups are to be compared in terms to time to first occurrence of any of the components of the composite primary endpoint. It is assumed that 5% of patients with primary outcome would have multiple events of both AIDS* and non-AIDS. Rates of non-AIDS morbidity were not available and the events in the cohorts used were not adjudicated. We assumed that the rate of non-fatal non-AIDS events was 4 times the death rate from non-AIDS causes resulting in an assumed ratio of non-AIDS to AIDS* events of 3.3. We also assumed that the percentage of accepted events after adjudication was 65% for AIDS* and 90% for non-AIDS events. The sensitivity of sample size to the ratio of non-fatal non-AIDS to non-AIDS death and to different adjudication rates are illustrated below in Table G-3. Sample size is shown assuming 90% power and a type 1 error of 0.05 (2-sided). Based on this table, the target number of events was set at 370. If 275 events are achieved instead of 370, power is approximately 0.80 to detect a hazard ratio of 0.714 at the 0.05 level of significance.

Table G-3: Sensitivity of Sample Size and the Event Target to Assumptions Concerning the Ratio of Non-AIDS to AIDS* Events and Event Adjudication Estimates

Ratio: Non-fatal Non-AIDS/Non-AIDS Deaths	% AIDS* Events Adjudicated	Composite Event Rate per 100 Person Years (Deferred Arm)	Hazard Ratio (average over follow-up)	Combined Sample Size	Event Target
3	65	2.40	0.706	4,244	351
4	65	2.81	0.712	3,822	369
5	65	3.23	0.717	3,472	383
3	75	2.49	0.700	3,900	333
4	75	2.91	0.707	3,545	353
5	75	3.33	0.712	3,245	367

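### The stated 0.73 power for non-AIDS events and deaths not attributable to AIDS does not follow from the plan's assumptions, which give about 0.67 (range 0.65 to 0.70)

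*Supplement*

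**What the plan says.** Section 3.5 sets out the design assumptions and then gives power for the two major components.

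- Error rate and power for the composite: "Type I error is 0.05 (2-sided) and power = 0.90".
- Allocation (Section 3.4): "Eligible participants will be randomized in a 1:1 ratio to either the early ART group or the deferred ART group".
- Size: "a sample size of 4,000 participants (2,000 in each treatment group) and a target of 370 primary events has been established as the initial goal".
- Composite effect: "early ART is predicted to reduce the primary endpoint rate by 28.8% compared to deferred ART".
- Split by type: "AIDS* events represent 23% of the events in the deferred arm, and early ART will reduce this hazard by 43" per cent. Non-AIDS events and deaths not attributable to AIDS make up the other 77% of deferred-arm events, with a 24% reduction.
- Component power, on the above assumptions with 370 primary events among 4,000 participants: "power is 0.74 to detect a 43% reduction in the hazard of AIDS*, and power is 0.73 to detect a 24% reduction" for the non-AIDS component.

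Item b ties the choice of 90% to these components: "Power was set at 90% for the primary endpoint, in part, to ensure that there would be adequate power to address the components". Appendix G adds one assumption that affects component counts: "It is assumed that 5% of patients with primary outcome would have multiple events of both AIDS* and non-AIDS". Neither Section 3.5 nor Appendix G derives the component powers separately.

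**The concern.** The two component powers stand in one sentence on one stated basis, so one method should return both. The non-AIDS component has many more events but a much weaker assumed effect. A quick check shows that 0.73 at a hazard ratio of 0.76 needs nearly as many events as the whole composite is planned to have.

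Non-AIDS events or death not attributable to AIDS is a major secondary endpoint and supplies most of the composite. If its power is overstated, a null result on it will be read as more informative than it is, and item b's reason for choosing 90% power looks stronger than the numbers allow.

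**Working it through.** **Inputs.** From Section 3.5: two-sided 0.05; deferred-arm shares 0.77 and 0.23; hazard ratios 0.76 (non-AIDS) and 0.57 (AIDS*); composite hazard ratio 0.712; 370 primary events; 4,000 participants; 3-year accrual and at least 3 years of follow-up; loss of 2.7 per 100 person-years. From Section 3.4: 1:1 allocation. From Appendix G: deferred-arm composite rate 2.81 per 100 person-years, and 5% of patients with a primary outcome having both event types.

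**Formula.** With d events, power = Φ(√(d/4) × |ln HR| − 1.96) (Schoenfeld).

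**The plan's other figures first.**
- Events for 90% power at HR 0.712: 365 (Schoenfeld) or 372 (Freedman). The plan states 369.
- 275 events at HR 0.714: √68.75 × 0.3369 − 1.96 = 0.833, power 0.798. Appendix G states about 0.80.
- AIDS*, 23% of 370 = 85 events at HR 0.57: √21.25 × 0.5621 − 1.96 = 0.631, power 0.74. The plan states 0.74.

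The method therefore returns the plan's other figures.

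**Non-AIDS events, three ways.**

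1. *Split the 370 events.* The composite hazard ratio implied by the components is 0.23 × 0.57 + 0.77 × 0.76 = 0.7163. Deferred-arm events are 370/1.7163 = 215.6. Non-AIDS events are 215.6 × 0.77 × 1.76 = 292, a pooled share of 0.790.
2. *Follow 4,000 participants.* With event hazard λ and loss hazard 0.027, the chance of an observed event is λ/(λ + 0.027) × [1 − exp(−(λ + 0.027)f)], averaged over f from 3 to 6 years. At 3,822 participants this gives 368 composite events (369 stated). At 4,000, with each component as its own endpoint, it gives about 308 non-AIDS and 85 AIDS* events.
3. *Add the overlap in full.* Scaling gives 369 × 4,000/3,822 = 386 composite events. Non-AIDS events are then 386 × (0.790 + 0.05) = 324. This is an upper limit, because it assumes that in every patient with both types the AIDS* event came first.

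**Power at HR 0.76 (|ln HR| = 0.2744).**

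| Basis | Non-AIDS events | √(d/4) × 0.2744 − 1.96 | Power |
|---|---|---|---|
| 370 split by type | 292 | 0.385 | 0.65 |
| 4,000 followed 3 to 6 years | 308 | 0.448 | 0.67 |
| 386 plus full 5% overlap | 324 | 0.510 | 0.695 |
| Stated | | | 0.73 |

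**What 0.73 would need.** d = 4 × (1.960 + 0.613)² / 0.2744² ≈ 352 events, and 352/370 = 95%. If all 370 events were non-AIDS, power would be 0.75. With 292 events, the hazard ratio would have to be about 0.74.

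**Both figures on one basis.** These bases give roughly the stated AIDS* power:
- Flat shares of 370: AIDS* 0.74 (85 events), non-AIDS 0.64 (285 events).
- The 4,000-participant model: AIDS* 0.735 (85 events), non-AIDS 0.67 (308 events).
- 370 split by type, plus 2.5% overlap to each component: AIDS* 0.746 (87 events), non-AIDS 0.66 (301 events).

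None gives 0.73 for non-AIDS. One-sided 0.05 gives 0.75 to 0.80 for non-AIDS and 0.80 to 0.90 for AIDS*, so it matches neither figure.

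**The case against.** The strongest reply is that 0.65 is too harsh and that rounding could explain much of the gap. The power sentence names 4,000 participants as well as 370 events, Section 3.3 analyses each component as its own time to first event, and Appendix G allows for patients with both types. Those points stand, and they are why 0.67 is the better central value, with 0.695 as the upper end at the stated effect.

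Rounding helps less. The printed components return 0.716, not 0.712. Holding the AIDS* terms, 0.712 implies a non-AIDS hazard ratio of (0.712 − 0.23 × 0.57)/0.77 = 0.754. That is a reduction of 24.6%, which would print as 25%. The smallest hazard ratio that prints as 24% is about 0.755. With 324 events it gives 0.716; even 0.754 gives only about 0.72. This stack also disturbs the other figure: AIDS* power becomes 0.805 if the full overlap is credited to AIDS* as well (101 events), or 0.717 if none is (81 events). The simulations in Appendix G supply event rates and average hazard ratios, but the text describes no separate simulation of component power.

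A reader might infer that the AIDS* figure is wrong too, because splitting 370 events gives 78 AIDS* events and power of 0.70. The documents do not support that. The 4,000 participants in the same sentence yield about 85 AIDS* events and power of 0.735, so 0.74 fits the stated basis.

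It is also fair that component power sets no sample size, test or stopping boundary. The DSMB guideline in Section 5.2 asks for consistent components, but component power is not an input to it.

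**Conclusion.** The concern holds for the non-AIDS component only. On the plan's assumptions its power is about 0.67, with a range of 0.65 to 0.70, against 0.73 stated. The chance of missing the planned 24% reduction is therefore about 33% (30% to 35%), not 27%. This rests on a constant hazard ratio of 0.76, two-sided 0.05, 1:1 allocation and the plan's own event split. The plan's simulated rates vary over time, so the second decimal should not be pressed.

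A reader might go further and conclude that the trial is undersized. That does not follow: the 369 events, 90% composite power and 0.80 at 275 events all reproduce. Nor can the power of the trial as finally sized be judged. The summary of changes says that Letter of Amendment 2 added a Section 5.3 with a new sample size and event target, but that text is not among the documents, so component power may have been restated there.

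**What to change.** - In Section 3.5, restate power for non-AIDS events and deaths not attributable to AIDS as about 0.67 (range 0.65 to 0.70) at 4,000 participants and 370 primary events. Alternatively, keep 0.73 and state the event count and hazard ratio that produce it.
- Leave the AIDS* figure of 0.74 as it is, and add the event count of about 85.
- In item b, temper the claim of adequate component power to match.
- If Section 5.3 has not already done so, recompute both component powers under the re-estimated event target.

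The cost is a text correction and a short calculation. One reported figure becomes less favourable; the design, the primary analysis and the event target do not change.
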